Our team is comprised of highly experienced adolescent HIV prevention researchers, including [name] and [name], who have a long history of research that seeks to address the key health issues facing South African adolescent girls while at the same time protecting this vulnerable population. The research sites have considerable experience in conducting clinical research in adolescent populations.

Figure 2. HIV incidence (%) by age and sex in South Africa

[figure not shown]
[figure not shown]

Figure 3. Adolescent pregnancy in South Africa, 2010-2013

Our study, PrEP-PP (PrEP in Pregnant and Postpartum women) will determine the distribution of women across the PrEP cascade (i.e. PrEP initiation, retention, and adherence) in a cohort of HIV- pregnant and breastfeeding adolescent girls and women in two public health facilities in South Africa to inform policymakers about the efficacy of PrEP integration into antenatal (ANC) and postnatal care in high HIV incidence communities.

2. Study objectives:

The objectives of the study are to:

1. Determine the distribution of women across the PrEP cascade:
 - (1) Evaluate the proportion of pregnant and breastfeeding women who initiate PrEP out of all women offered PrEP
 - (2) Evaluate the proportion of pregnant and breastfeeding women who are retained in the PrEP cohort
 - (3) Evaluate the proportion of pregnant and breastfeeding women who initiate PrEP who adhere to PrEP using objective dried blood spot measures and subjective measures of self-reported pill count and adherence
 - (4) Evaluate the proportion of pregnant and breastfeeding women on PrEP (and not on PrEP) who acquire HIV, who transmit HIV to their infant, and who report adverse events
2. Evaluate patient and provider-level factors associated with the PrEP cascade using quantitative and qualitative approaches (including in-depth interviews)

3. Study design

To address these objectives, we will conduct an observational cohort study in 220 pregnant women who will be recruited at the first antenatal care (ANC) visit from the Gugulethu Midwife Obstetric Units in Cape Town. We will follow the enrolled women through 12-months post-delivery.

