- **DBS:** Dried blood spots will be prepared from finger pricks every two months in women on PrEP to evaluate adherence.
 - DBS cards will be prepared and stored following standard protocols and stored at -80°C for analysis at the end of the study with the clinical pharmacodynamic laboratory of [name] at UCT. Using techniques developed by [name] at University of Colorado [16] adherence will be defined as red blood cells containing TDF-DP ≥ 40 ng/dl which is indicative of daily dosing [16]. As supplementary measures of PrEP adherence, we will use self-reported items that we will adapt from previous studies (including visual analogue scales as well as 3-day, 30-day and last visit recall questionnaires) (22-25), and pharmacy refill records to compare objective versus subjective measures and report on the effectiveness of each measure in correlation to the true measures of TDF-DP. We will determine final dosing and measures following reporting from ongoing PK studies of pregnant women on PrEP (e.g. Impaact 2009).

Laboratory tests in all women in the cohort:

- **STI testing (baseline, 3rd trimester and first postpartum visit):** Self-collected vaginal swab kits will be provided to all participants along with an explanation for their use. Swabs will be analyzed using on-site testing equipment (GeneXpert; Cepheid ®) for rapid testing of chlamydia, gonorrhoea and trichomonas vaginalis. If they test positive, they will be treated by the nurse/midwife in ANC or postpartum care and a referral for her partner to receive STI treatment in the clinic.
- **HIV testing.** As part of the standard of care, all pregnant and breastfeeding women will be tested for HIV using serial rapid HIV tests at each antenatal and postnatal care visit. In addition, PrEP-PP study staff will have a stock of rapid HIV test kits to ensure that women get tested at each study visit.
 - **Seroconversion.** If a woman, infant or partner seroconverts at any point during the study, they will be referred to the clinician on duty to initiate ART, following counseling about PMTCT, breastfeeding, disclosure, and ART adherence, per the SA National Protocols [17]. Seroconverted women will be censored from the remainder of the study and referred to the clinic to initiate ART.

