The primary analysis will focus on measuring the distribution of women across the PrEP cascade including: initiation, retention and adherence. **PrEP initiation** will be based on a woman’s uptake of PrEP and allow for stoppage and re-initiation; **PrEP retention** will be defined as not missing >1 visit among those on PrEP (with separate analyses of PrEP stoppage). For **PrEP adherence** for women on PrEP we will measure both **perfect adherence** (i.e. level of objective adherence throughout pregnancy and breastfeeding periods) as well as “**prevention-effective**” adherence (i.e. adherence before and during times of sexual activity) in participants through objective and subjective measures to evaluate agreement between the two measures, and the level of under- or over-reporting. Primary adherence analyses will use objective measures (TDF-DP from DBS) taken on all those who enrolled and initiated PrEP; subsidiary analyses will consider (i) other adherence measures and (ii) multiple imputation for missing adherence data.

- **Use of PrEP will be measured** through alternate definitions of the main outcomes (e.g. adherence by self-report versus adherence by pharmacy refill), compared using measures of agreement and will be analyzed as independent models to contrast estimated associations.

- **Measurement of prevention-effective execution:** Execution refers to PrEP adherence during a time when at-risk sex happens. It is calculated by: number of doses reported, or recorded/number of expected doses based on HIV risk and PrEP initiation/discontinuation
- **Prevention-effective continuation:** Prevention-effective continuation describes the duration of PrEP use during periods of HIV risk and references the absolute time of use during pregnancy and breastfeeding periods. We will adapt the methodology from previous PrEP studies in SA including FEM-PrEP to create a semi-ordinal composite adherence score from blood specimens from DBS every 2-months.

Table 2: Study measures for PrEP-PP

Primary Outcomes	Measurement	Source	Frequency
PrEP initiation	# of women who initiate PrEP over time / total # of women in active cohort = proportion of women who initiate PrEP	Electronic provider log (REDCap)	Daily entry, weekly analysis

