Each outcome will be described via cumulative incidences at fixed intervals (e.g., cumulative PrEP initiation by delivery) and incidence densities over time. The general statistical approaches to these outcomes are analogous; data will be described graphically, including product-limit graphs, with preliminary analyses based on standard approaches for rates and proportions. The modelling approach will vary depending on the nature of the outcome. **PrEP initiation** will be modelled using a probit model (preferred to estimate risk factors for common outcomes) with individual-level covariates as fixed effects; when time-dependent or visit-specific covariates are included in the analysis of cumulative initiation we will shift to a mixed-effects setting with random effects around individual participants. **PrEP retention** will be examined using similar approaches; in addition, we will use time-to-event methods to estimate factors associated with time to loss (non-retention) among women having initiated PrEP. **PrEP adherence** will be modelled using mixed effects probit models as above and generalized estimating equations to examine the marginal effect of individual-level covariates on adherence during the study [85]. Throughout, robust estimates of standard errors will be used.

The same modelling approaches will be used to explore secondary implementation questions such as the effect of individual, pill/study, and disease factors on PrEP initiation, retention and adherence outcomes (see Figure 1 for conceptual model). The main exposures include: **individual level factors**: risk perception, community/family support, sexual activity, risk, concerns about drug's side effects and harm on self (pregnancy) and/or infant's health. **Pill regimen and study factors** include: PrEP side effects, time required to participate in study, patient-provider relationship measured from the participants' perspective. **Disease factors** include: stigma around HIV and PrEP, and partner's HIV status (see Table 5 for specific variables).

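### Product-limit graphs of cumulative PrEP initiation, with censoring at seroconversion and exit, lie at or above the proportion of all women offered PrEP who start; Table 2's denominator needs aligning too

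*Combined protocol and SAP*

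**What the plan says.** Objective 1(1) in section 2 sets the target: "Evaluate the proportion of pregnant and breastfeeding women who initiate PrEP out of all women offered PrEP".

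Section 6 (Statistical analysis considerations) states: "Each outcome will be described via cumulative incidences at fixed intervals (e.g., cumulative PrEP initiation by delivery) and incidence densities over time". It calls the approaches to the outcomes analogous and continues: "data will be described graphically, including product-limit graphs", alongside preliminary analyses by the usual methods for rates and proportions. Initiation is then modelled with a probit model. Time-to-event methods are named explicitly only for retention.

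Table 2 measures the primary initiation outcome as the number "of women who initiate PrEP over time / total # of women in active cohort = proportion of women who initiate PrEP". The plan does not define the active cohort.

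Section 4 lists the reasons for censoring: seroconversion, moving away, transfer out of care, and loss to follow-up (which includes no longer wanting to take part). Section 5, under HIV testing, repeats the first: "Seroconverted women will be censored from the remainder of the study and referred to the clinic to initiate ART". PrEP is first offered at enrolment (section 5, Step 11) and offered again to non-users at every follow-up visit, so a woman can start late or leave before starting. No method for competing events is named.

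**The concern.** A product-limit estimate treats a censored woman as if she would go on to start at the same rate as the women still followed. For a woman who seroconverts this is untrue: she is taken out of follow-up and referred for ART, so a first PrEP start is no longer possible. For a woman who moves, transfers or is lost, a later start is possible but the study does not observe it. She still belongs to the Objective 1(1) denominator.

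One minus product-limit therefore describes initiation in a hypothetical cohort with no exits. It cannot fall below the observed proportion of all women offered PrEP. Initiation is the first step of the cascade, and the plan intends the cascade to inform policy. A curve that disagrees with the tabulated proportion, always in the favourable direction, would need an explanation that the plan does not provide.

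**Working it through.** The plan gives no initiation, deferral or dropout rate, so there is no figure of its own to reproduce. The check has three parts.

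**1. Direction.** With no censoring, one minus product-limit equals starters divided by all women offered PrEP. With censoring, the method passes each censored non-starter's weight to women who remain at risk, so the estimate is higher as soon as any of them starts later. This needs no assumption about rates.

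**2. Size.** Women who start at enrolment count the same in both estimators, so the excess arises only among deferrers and scales with the deferral fraction. With constant monthly rates *s* (start) and *c* (seroconversion plus other exit) and horizon *T* months:

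- One minus product-limit: 1 − exp(−*sT*)
- Cumulative incidence with exits competing: *s*/(*s*+*c*) × [1 − exp(−(*s*+*c*)*T*)]
- Overall excess: deferral fraction × the difference

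Inputs:

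- HIV incidence of 10.7 to 12.4 per 100 person-years, from the background section, applied to women not on PrEP: 0.107/12 = 0.0089 and 0.124/12 = 0.0103 per month.
- Other exits of 10 to 30% per year (assumed): −ln(0.9)/12 = 0.0088 and −ln(0.7)/12 = 0.0297 per month. Hence *c* runs from 0.0177 to 0.0401.
- Deferral at enrolment of 30 to 50% (assumed).
- Later start *s* of 0.03 to 0.10 per month (assumed).
- *T* = 6 for delivery and 18 for study end, following the layout of Table 1.

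| Horizon, exits | *s* | *c* | One minus PL among deferrers | Cumulative incidence among deferrers | Difference | Deferral | Overall excess |
|---|---|---|---|---|---|---|---|
| 6, all | 0.03 | 0.0177 | 16.47% | 15.65% | 0.82 | 30% | 0.2 |
| 6, all | 0.10 | 0.0401 | 45.12% | 40.59% | 4.53 | 50% | 2.3 |
| 18, all | 0.03 | 0.0177 | 41.73% | 36.24% | 5.48 | 30% | 1.6 |
| 18, all | 0.10 | 0.0401 | 83.47% | 65.66% | 17.81 | 50% | 8.9 |
| 18, seroconversion only | 0.03 | 0.0089 | 41.73% | 38.83% | 2.90 | 30% | 0.9 |
| 18, seroconversion only | 0.10 | 0.0103 | 83.47% | 78.20% | 5.27 | 50% | 2.6 |

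A central case has *s* = 0.06 and 20% per year other exits, so *c* = 0.0089 + 0.0186 = 0.0275. At month 18 it gives 66.0% against 54.4% among deferrers: 3.5 points overall at 30% deferral and 5.8 at 50%. Seroconversion alone at month 6 gives 0.1 to 0.6 points.

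A separate calculation on the Table 1 visit grid used wider assumptions: 30 to 90% start at enrolment, 5 or 15% of the rest start per month, and 2 to 5% of non-starters leave per month. It gave 0.2 to 5.8 points at month 5 after enrolment and 1.2 to 17.9 at month 17. If 90% start at enrolment, the excess is at most 0.8 and 2.6 points.

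**3. The two denominators.** Take 220 women with assumed counts: 154 start at enrolment; over five later visits 25 more start, 4 non-starters seroconvert and 20 leave. Spread evenly, each visit has 5 starts and 4.8 exits, and the numbers at risk are 66, 56.2, 46.4, 36.6 and 26.8.

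- Starters / all offered: 179/220 = 81.4%.
- One minus product-limit, starts counted before exits at each visit: 1 − 0.300 × (61/66)(51.2/56.2)(41.4/46.4)(31.6/36.6)(21.8/26.8) = 84.2%.
- Aalen-Johansen with seroconversion competing and leavers counted as not initiated: 25 later starts among 66, so (154 + 25)/220 = 81.4%.
- Table 2 proportion if the 24 who exit leave the denominator: 179/(220 − 24) = 179/196 = 91.3%.

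**The case against.** The strongest reply is that product-limit is named only for graphs. The defined primary measure is a simple proportion, initiation is modelled by probit, and the estimator for the fixed-time cumulative incidences is not named. A reader might infer that the primary uptake figure itself is a product-limit estimate and therefore inflated. The documents do not support that. What remains is the curve, plus any fixed-time value read from it, which is a natural reading because no other estimator for censored data is given.

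Second, the exits differ in kind. Seroconversion is a true competing event. A woman who moves or transfers could start PrEP elsewhere, and censoring her answers a legitimate but different question. A reader might treat every exit as the same error. It is fairer to call the handling of leavers an estimand choice, which Objective 1(1) settles by putting all women offered PrEP in the denominator. Most of the upper range comes from these assumed exits.

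Third, the plan lets initiation include stoppage and re-initiation, so a first-start curve is an interpretation. That stands, and the fix should say first initiation.

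Fourth, the effect is small where the plan points. By delivery it is 0.2 to 2.3 points, whereas for an illustrative 80% uptake in 220 women the 95% half-width is 1.96 × √(0.8 × 0.2/220) = 5.3 points. The study also describes itself as a pilot. This limits the importance of the point, but a bias of known direction that can be removed at no cost is still worth removing.

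Fifth, one could say that with all exits competing the Aalen-Johansen estimate merely returns the simple proportion. It does when follow-up is otherwise complete to that time, which shows that the corrected curve hits the stated target.

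**Conclusion.** The point holds as a minor one. The direction is certain: with the stated censoring, a product-limit curve of initiation lies at or above starters out of all women offered PrEP. The size is not certain. About 0.2 to 2.3 points by delivery and 1.6 to 8.9 by month 18 rest on assumed deferral, start and exit rates; only the HIV incidence comes from the documents, and applying it to women not on PrEP is itself an assumption. Seroconversion alone accounts for 0.9 to 2.6 points at month 18. If most women start at enrolment, the excess is smaller still.

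The Table 2 denominator is the more direct departure from Objective 1(1), but only if active cohort excludes women who have left, which the plan does not say. In the illustrative cohort that reading moves the proportion more (91.3% against 81.4%) than the curve does (84.2%).

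**What to change.** In section 6, state that time from offer to first initiation will be shown as a cumulative incidence (Aalen-Johansen) curve. Seroconversion before starting is a competing event, and women who leave before starting are counted as not initiated in the study. Fixed-time values should be read from that curve. Follow-up that ends as planned at 12 months postpartum can still be censored; the curve equals starters over all women offered PrEP up to the time by which such censoring begins.

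In Table 2, replace the active cohort with all women offered PrEP as the denominator of the initiation proportion, so that table, curve and Objective 1(1) agree.

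The cost is a few sentences of text; the data and software are unchanged. The uptake figure becomes slightly less favourable, and starts elsewhere after leaving are not counted, which the report should say.

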Step 1: In ANC: Healthcare providers provide counseling on HIV prevention and treatment at each ANC visit including HIV testing, as part of standard of care. In post-natal care and well-baby visits women may not receive regular HIV testing and messages and will receive this within step 2 (with study counselor). Following their ANC visit, enrolled women will be invited to attend the study site in each MOU to do the follow-up visit including the ACASI survey and prescription and adherence counseling (if on PrEP).

Step 2: ACASI survey at each visit in a private study room

Step 3: In the study room, the study counselors will provide PrEP-specific counseling including adherence counseling for those on PrEP (and management of side effects), or counseling about the risks and benefits of PrEP for women not yet on PrEP. Women not on PrEP will be asked if they are interested in starting PrEP at this visit.

Step 4: STI testing: At 3rd trimester visit and first postpartum visit, participants self-collect a vaginal swab for STI testing (chlamydia, gonorrhea and trichomonas vaginalis using Cepheid® point of care testing). Participants will be treated if diagnosed with a STI according to National Guidelines. They will receive a partner notification letter to bring their partner in for treatment as well.

Step 5 (for women on PrEP): At each visit the study counselor will ask, and record responses, all participants on PrEP about any side effects associated with TDF/FTC, including diarrhea, nausea, fatigue, headache and rash (which are seen in about 10% of participants during the initiation of therapy). We will encourage participants to contact the study nurse if they experience side effects between visits.

For participants on PrEP, the study nurse performs a blood draw for creatinine clearance and a finger prick for DBS testing for adherence measures and (if applicable for this visit). See Table 1 for study calendar.

Step 6: PrEP provision (for 1 or 2 months) and appointment reminder

Follow-up & retention: Tracing information will be taken at the enrolment visit and updated at each study visit. Retention activities will focus on scheduled measurement visits. Following our established approach in this setting, we will provide reminder calls to participants before their measurement visits, and initiate tracing, including home visits, for women who do not attend the measurement visit within one week of the scheduled visit.

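### The initiation model with visit-specific covariates sets no at-risk visits and no covariate timing, so values recorded after starting PrEP, including side effects, can appear to predict starting

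*Combined protocol and SAP*

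**What the plan says.** All of this is in the combined protocol and SAP.

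- **Outcome scale** (Section 6, Statistical analysis considerations): "Each outcome will be described via cumulative incidences at fixed intervals (e.g., cumulative PrEP initiation by delivery"). Table 2 measures initiation as the number "of women who initiate PrEP over time / total # of women in active cohort". The same section says that initiation "will be based on a woman’s uptake of PrEP and allow for stoppage and re-initiation", but not how stopping and restarting enter the cumulative outcome.
- **Model**: a probit with individual-level fixed effects by default. However, "when time-dependent or visit-specific covariates are included in the analysis of cumulative initiation we will shift to a mixed-effects setting", with random effects for participants.
- **Exposures**: the same approaches are to explore "the effect of individual, pill/study, and disease factors on PrEP initiation, retention and adherence outcomes". The pill and study factors are "PrEP side effects, time required to participate in study, patient-provider relationship measured from the participants' perspective". Concern about side effects is listed separately, among the individual-level factors.
- **Collection**: at follow-up visits (Section 5, Step 5) the counsellor asks "all participants on PrEP about any side effects associated with TDF/FTC". The survey measures under Sources of data add symptom schedules for mothers at every study visit. Women not on PrEP are offered it again at each follow-up visit (Step 3), so starts after baseline are part of the design.
- **Time-to-event methods** are named for time to loss among women who have started, not for starting.

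**The concern.** Whether a woman has ever started by a given visit cannot go back to no. If that status is the response at every visit, each visit after her first start is a further row with outcome 1, and the covariates on that row were measured after the event they are meant to explain. Any factor that shifts once a woman is taking PrEP would then look like a reason for starting. Risk perception, stigma, partner or family support and the relationship with providers could plausibly do so, since PrEP users receive adherence counselling and the survey is repeated at each visit.

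Experienced side effects are the clearest case, because they cannot occur before first use. Objective 2 asks which factors are associated with the cascade, and the pilot is meant to inform later work. A factor that follows initiation could be carried forward as one that drives it.

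**Working it through.** The plan states no figure for this model, so there is none to reproduce. The checks use simple null cases.

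**1. Crude size, any covariate that changes after starting.** From the documents: 12 survey visits (Table 1, months 1–7, 9, 11, 13, 15 and 18). Assumed, because the documents give no rates: a proportion p starts at baseline; a proportion h of those remaining starts at each later visit; the covariate has prevalence 30% up to and including the start visit and q afterwards, and has no influence on starting.

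Shares of all person-visits:
- before start: n = (1 − p)/12 × [1 − (1 − h)^12]/h
- at the start visit: s = [1 − (1 − p)(1 − h)^11]/12
- after start: a = 1 − n − s

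With p = 0.50 and h = 0.08: n = 0.3293, s = 0.0667, a = 0.6040. With q = 0.50:
- P(started | covariate present) = (0.3s + 0.5a)/(0.3(n + s) + 0.5a) = 0.3220/0.4208 = 0.765
- P(started | covariate absent) = (0.7s + 0.5a)/(0.7(n + s) + 0.5a) = 0.3487/0.5792 = 0.602
- difference = 0.163

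Simulating 400 cohorts of 220 women under these rates also gave 0.163. Differences over the range of assumptions, in percentage points:

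| Start at baseline | Start per later visit | q = 35% | q = 40% | q = 50% |
|---|---|---|---|---|
| 30% | 4% | 5.1 | 9.8 | 18.7 |
| 30% | 8% | 5.0 | 9.7 | 18.5 |
| 50% | 8% | 4.5 | 8.6 | 16.3 |
| 80% | 8% | 2.3 | 4.4 | 8.4 |
| 90% | 4% | 1.5 | 2.9 | 5.5 |
| 90% | 8% | 1.3 | 2.4 | 4.5 |

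The range is about 1 to 19 points. On visits up to and including the first start, the covariate has prevalence 30% whether or not the woman starts, so the expected difference is 0 by construction.

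**2. Side effects, probit models.** From the documents: 220 women, the same 12 visits, and side effects in about 10% during initiation of therapy. Assumed: 30%, 60% or 80% start at baseline, then 10% per later visit; background symptoms in 0%, 5% or 15% of visits; side effects either at the first visit after starting only, or at 10% of all later visits. The true effect on starting is zero. There were 200 runs per scenario, using a pooled probit with cluster-robust standard errors.

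- *Recorded only in users (0% background):* every visit with a side effect already has outcome 1. Separation occurred in 100% of runs, so no finite coefficient exists.
- *Recorded in all mothers, side effects at the first visit after starting only:* mean coefficient +0.04 to +0.15; P < 0.05 in 9% to 28% of runs.
- *Recorded in all mothers, persistent side effects:* mean coefficient +0.28 to +0.62; P < 0.05 in 88% to 100% of runs.
- *At-risk visits only, symptom recorded before the offer (5% or 15% background):* mean coefficient −0.05 to +0.01; P < 0.05 in 3% to 10% of runs.

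**3. The planned random-intercept probit.** Two scenarios (30% and 60% starting at baseline, 5% background, persistent side effects), 10 runs each: mean coefficients +0.36 and +0.20, median z 1.18 and 0.36, random-effect SD about 6.5 to 7. So large an SD suggests that the intercept mostly absorbs an outcome that never reverses. In the second scenario the mean z was implausible, a sign that the standard error failed in at least one run. These results are indicative only.

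**The case against.** The strongest reply is that the harmful layout is inferred. The plan does not say that visits after first start stay in the initiation model, and random effects with visit-specific covariates could also describe person-visits up to first start. That is fair. Keeping every visit is the natural reading of cumulative status with participant random effects, but not the only one.

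Four stronger readings are tempting, and the documents do not support them.

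- *The modelled outcome is strictly irreversible.* This is true of ever having started, but the definition also allows stopping and restarting and leaves their place open. Earlier side effects could legitimately predict re-initiation.
- *Side effects will certainly enter the first-initiation model.* The exposure list is pooled across three outcomes and does not assign each factor to each model. Table 5, cited for the specific variables, is not in the text available for this review, so the covariates of each model cannot be checked. What stands is that initiation is named and no exception is made.
- *Perfect separation is inevitable.* It follows if only users are asked. If the symptom schedules cover all mothers, the result is bias instead.
- *A 16-point error is expected.* That is one crude pooled difference under assumed rates, not a coefficient of the planned model, which gave a weaker signal that was usually not significant.

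It is also true that the shift is conditional on such covariates being used, and that the factor models are secondary in a pilot said not to be powered for differences. Low power limits precision; it does not excuse an association that runs backwards in time.

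**Conclusion.** The concern holds in a limited form. The plan names a method for cumulative initiation with visit-specific covariates and gives neither the visits at risk nor the time order of covariates. Followed on its natural reading, it lets values recorded after starting predict starting. Experienced side effects have no estimable effect on first initiation if only users are asked, and a biased one if all mothers are asked.

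The direction comes from the data structure. The size comes from assumptions: about 1 to 19 points crude with 30–90% starting at baseline, 4–8% starting per later visit and a post-start rise from 30% to 35–50%. The planned model's own distortion may be smaller and is poorly determined here. The descriptive proportion initiating, and the primary description of the cascade, are unaffected.

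**What to change.** In Section 6, state that when time-dependent covariates are used:

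1. First initiation is a discrete-time model on person-visits up to and including the first start, with terms for baseline and visit. The probit link can stay.
2. Covariates are those measured before that visit's offer. The survey already precedes it (Step 7 before Step 11 at enrolment; Step 2 before Step 3 at follow-up), so same-visit survey answers qualify.
3. Experienced PrEP side effects are removed from the first-initiation exposures. Concern about side effects, measured before the offer, stays.
4. Experienced side effects are used for stopping, retention and adherence, and for re-initiation. Re-initiation is modelled separately among women who stopped, or described if there are few.

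The cost is SAP wording and a little more analysis work, with the same data and software. The initiation model will have fewer person-visits, because visits after first start carry no information about first starting.
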